5. GENERAL METHODOLOGY AND CONVENTIONS

5.1. Hypotheses and Decision Rules

Hypothesis testing will be performed to assess noninferiority, comparing the 20vPnC/saline vaccine group against the 13vPnC/PPSV23 vaccine group for each of the 20 serotype-specific OPA titers.

A 2-fold margin will be used for each of the noninferiority hypothesis test.

5.1.1. Hypothesis Testing

Hypothesis testing will be performed to assess noninferiority by comparing the serotype-specific OPA titers of the 20vPnC/saline group to those from the 13vPnC/PPSV23 group. The null hypothesis for each serotype-specific OPA titer is:

$$H_0: \ln(\mu_A) - \ln(\mu_B) \leq \ln(0.5)$$

where $\ln(0.5)$ corresponds to a 2-fold margin for the assessment of noninferiority.

- $\ln(\mu_A)$ is the natural log of the serotype-specific OPA GMT 1 month after 20vPnC administration for the 20vPnC/saline group.
- $\ln(\mu_B)$ is the natural log of the serotype-specific OPA GMT 1 month after 13vPnC administration for the 13vPnC/PPSV23 group when the endpoint is the serotype-specific OPA GMT from 1 of the shared 13 serotypes in 13vPnC, or,
- $\ln(\mu_B)$ is the natural log of the serotype-specific OPA GMT 1 month after PPSV23 administration for the 13vPnC/PPSV23 group when the endpoint is the serotype-specific OPA GMT from 1 of the 7 additional serotypes.

Noninferiority for serotype-specific OPA titers will be formally evaluated by a 2-sided 95% CI for the ratio of serotype-specific OPA GMTs (the 20vPnC/saline group to the 13vPnC/PPSV23 group) with results from 1 month after vaccination with 20vPnC (Visit 2) and 1 month after vaccination with 13vPnC (Visit 2) for the 13 matched serotypes. For the 7 additional serotypes, the GMR will be calculated for the ratio of serotype-specific OPA GMTs from the 20vPnC/saline group at Visit 2 to that from the 13vPnC/PPSV23 group at Visit 3. Noninferiority for a serotype will be declared if the lower bound of the 2-sided 95% CI for the ratio of $\text{GMT}_{20vPnC/\text{saline}}$ to $\text{GMT}_{13vPnC/\text{PPSV23}}$ for that serotype is greater than 0.5 (2-fold criterion).

5.2. General Methods

Time points for local reactions and systemic events refer to data within 10 and 7 days after vaccination at Visit 1 and Visit 2 (for participants at Japan sites only), respectively.

Prompted local reactions, prompted systemic events, and AEs will be summarized after each vaccination at Visit 1 and Visit 2 by vaccine group.

CIs for all endpoints in the statistical analysis will be presented as 2-sided at the 95% level.

5.2.1. Analyses for Binary Endpoints

Descriptive statistics for categorical variables (eg, proportions) are the percentage (%), the numerator (n) and the denominator (N) used in the percentage calculation, and the 95% CI where applicable.

The exact 95% CI for binary endpoints for each vaccine group will be computed using the F distribution (Clopper-Pearson).¹ The 95% CI for the between-group difference for binary endpoints will be calculated using the Miettinen and Nurminen method.²

The 3-tier approach will be used to summarize AEs. For both Tier 1 (if any are identified during the study) and Tier 2 events, a 95% CI for the between-group difference in proportions will be calculated based on the Miettinen and Nurminen method. In addition, for Tier 1 events (if any), the asymptotic p-values will also be presented for the difference in proportions, based on the same test statistic and under the assumption that the test statistic is asymptotically normally distributed. For Tier 3 events, counts and percentages for each vaccine group will be provided.

5.2.2. Analyses for Continuous Endpoints

Unless otherwise stated, descriptive statistics for continuous variables are n, mean, median, standard deviation, minimum, and maximum.

Continuous immunogenicity outcomes of serotype-specific OPA titers will be analyzed on the natural log scale, and the results will be reported on the original scale after back transformation.

5.2.2.1. Geometric Mean Titers

For immunogenicity results of serotype-specific OPA titers, the geometric means will be computed along with associated 95% CIs. The GMTs and associated 2-sided 95% CIs will be calculated as the means and CIs of the assay results on the natural logarithmic scale based on the t-distribution, and then exponentiating the results.

5.2.2.2. Geometric Mean Ratios

The OPA serotype-specific antibody titer ratios (GMRs) will be calculated for each of the noninferiority assessments as:

The GMT ratio of 20vPnC/saline to 13vPnC/PPSV23:

- ratio of the GMT from the 20vPnC/saline group to that from the 13vPnC/PPSV23 group at Visit 2 for the 13 matched serotypes.

- ratio of the GMT from the 20vPnC/saline group at Visit 2 to that from the 13vPnC/PPSV23 group at Visit 3 for the 7 additional serotypes.

Details regarding the derivation of GMRs are provided below in Table 6.

Table 6. Derivation of Serotype-Specific OPA GMRs at 1 Month After Vaccination

Comparison	Analysis Population	Serotypes	Numerator	Denominator
Between-vaccine group comparison	Evaluable 13-matched immunogenicity population	13 matching serotypes	20vPnC/saline group at Visit 2	13vPnC/PPSV23 group at Visit 2
	Evaluable 7-additional immunogenicity population	7 additional serotypes	20vPnC/saline group at Visit 2	13vPnC/PPSV23 group at Visit 3

Abbreviations: GMR = geometric mean ratio; OPA = opsonophagocytic activity.

For each comparison above, there will be 2 approaches to calculating the GMR and CI for each serotype:

Model-Based GMR

The primary approach will be based on a linear regression model. Specifically,

- For the comparison of OPA results, the following terms will be included in the regression model: corresponding baseline OPA titer, age, sex (male or female), country (Japan, Korea, or Taiwan), smoking status (current smoker, ex-smoker, or never smoked), and vaccine group.

The difference between these LS means of OPA titers on the natural log scale and associated CI estimated from the linear regression model will be exponentiated to obtain the GMR and CI.

CCI

[figure not shown]
A 2-sided 95% CI will be used for the noninferiority comparison of the 20vPnC/saline group to the 13vPnC/PPSV23 group.

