## 9.4. Statistical Analyses

The SAP will be developed and finalized before database lock for the final analysis. The SAP will describe the participant populations to be included in the analyses, and procedures for accounting for missing, unused, and spurious data. This section is a summary of the planned statistical analyses of the primary, secondary, CCI [REDACTED] endpoints.

All CIs in the statistical analysis will be calculated as 2-sided at the 95% level.

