Secondary immunogenicity	
 
• GMTs of pneumococcal serotype-specific OPA titers 1 month after vaccination
 
 
OPA GMTs at 1 month after 20vPnC for the 20vPnC/saline vaccine group and 13vPnC (Visit 2) for the 13vPnC/PPSV23 vaccine group will be summarized for the 13 matched serotypes in each vaccine group. For the 7 additional serotypes, the GMTs at 1 month after 20vPnC (Visit 2) for the 20vPnC/saline vaccine group and the GMTs at 1 month after PPSV23 (Visit 3) for the 13vPnC/PPSV23 vaccine group will be summarized.
 
GMTs and the associated 2-sided 95% CIs will be derived by calculating means and CIs on the natural log scale based on Student's t-distribution, and then exponentiating the results.
 
 
• GMFRs of pneumococcal serotype-specific OPA titers
 
 
OPA GMFRs from before vaccination (Visit 1) to 1 month after 20vPnC or 13vPnC (Visit 2) for the 13 matched serotypes in each vaccine group will be summarized. For the 7 additional serotypes, the GMFRs from before vaccination (Visit 1) to 1 month after 20vPnC (Visit 2) for the 20vPnC/saline vaccine group and the GMFRs from before vaccination (Visit 1) to 1 month after PPSV23 (Visit 3) for the 13vPnC/PPSV23 vaccine group will be summarized. GMFRs will be limited to participants with nonmissing values both before any vaccination and after the indicated vaccination.
 
The GMFR for each serotype will be calculated as the mean of the difference of logarithmically transformed assay results (later time point – earlier time point) and transformed back to the original scale. Two-sided 95% CIs will be obtained by calculating CIs using Student's t-distribution for the mean difference of the

[figure not shown]
Endpoint	Statistical Analysis Methods

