3.1.2. Primary Immunogenicity Endpoint

- Serotype-specific OPA titers 1 month after vaccination.

OPA titers for the 20 pneumococcal serotypes (1, 3, 4, 5, 6A, 6B, 7F, 8, 9V, 10A, 11A, 12F, 14, 15B, 18C, 19A, 19F, 22F, 23F, and 33F) will be determined for all participants prior to vaccination at Visit 1 and at Visit 2 (approximately 1 month after Visit 1). OPA titers will be

determined only for the 7 additional serotypes at Visit 3 (approximately 1 month after Vaccination 2).

OPA titers above the LLOQ are considered accurate and their quantitated values will be reported. OPA titers below the corresponding LLOQ or denoted as BLQ will be set to $0.5 \times \text{LLOQ}$ for analysis. Missing assay results will not be imputed.

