4. ANALYSIS SETS (POPULATIONS FOR ANALYSIS)

Analysis populations are defined for the statistical analysis of safety and immunogenicity results in the table below. For the specified criteria in each population definition that are not associated with unblinded information (randomized or actual received vaccination), data for all participants will be assessed to determine if participants meet the criteria for inclusion in each analysis population prior to unblinding and releasing the database for the specified analysis, and the classifications will be documented per standard operating procedures.

Population	Description
Enrolled	All participants who sign the ICD.
Randomized	All participants who are assigned a randomization number in the IWR system.
Evaluable 13-matched immunogenicity	
This population was the primary analysis population for immunogenicity results of the 13 matched serotypes.
 
This population generally includes any randomized participant who:
 
 • is eligible based on inclusion and exclusion criteria • receives the first vaccine (20vPnC or 13vPnC) as randomized • has the Visit 2 blood collection within 27 to 49 days after Vaccination 1 • has at least 1 valid OPA titer for any of the 13 matched serotypes at Visit 2 • has no other major protocol deviations as determined by the clinician.

Population	Description
Evaluable 7-additional immunogenicity	
This population is the primary analysis population for immunogenicity results of the 7 additional serotypes.
 
This population generally includes any randomized participant who:
 
 • is eligible based on inclusion and exclusion criteria • receives the assigned investigational products at Visit 1 (20vPnC) for the 20vPnC/saline group or receives the assigned investigational products at both Visit 1 and Visit 2 (13vPnC and PPSV23) for the 13vPnC/PPSV23 group • has either the Visit 2 blood collection within 27 to 49 days after Vaccination 1 (20vPnC) for the 20vPnC/saline group or the Visit 3 blood collection within 27 to 49 days after Vaccination 2 (PPSV23) for the 13vPnC/PPSV23 group • has at least 1 valid OPA titer for any of the 7 additional serotypes at either Visit 2 for the 20vPnC/saline group or Visit 3 for the 13vPnC/PPSV23 group • has no other major protocol deviations as determined by the clinician.
CCI	
Safety	All participants who receive at least 1 dose of the investigational product.

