5.3. Methods to Manage Missing Data

A partial AE start date (missing day, missing both month and day) will be imputed by assigning the earliest possible start date using all available information, such as the stop date of the AE and the vaccination date(s) from the same participant, following the Pfizer standard of handling incomplete AE start date. A complete missing start date for an AE is not allowed in the data collection. No additional imputation will be applied unless stated otherwise (see [Section 3](#)).

The LLOQ for each assay will be provided by Vaccine Research & Development as part of the electronic data transfer or within the Clinical Testing Completion Memo prior to any statistical analysis of immunogenicity data. Assay results above the LLOQ will be reported, and values below the LLOQ, denoted as BLQ, will be set to $0.5 \times \text{LLOQ}$ for analysis.

CCI

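### Does the primary GMR model need a stated rule for evaluable participants who have no valid baseline OPA titer for a serotype?

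*SAP*

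**What the plan says.** SAP 5.2.2.2 makes a linear regression the primary approach to each serotype's GMR and states that "the following terms will be included in the regression model: corresponding baseline OPA titer, age, sex (male or female), country", followed by smoking status and vaccine group. SAP 6.1.2.1 and Protocol 9.4.1 give the same model.

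SAP section 4 sets a looser condition on titers. For the 13 matched serotypes a participant qualifies if he or she "has at least 1 valid OPA titer for any of the 13 matched serotypes at Visit 2". For the other seven the condition is that he or she "has at least 1 valid OPA titer for any of the 7 additional serotypes" at Visit 2 or Visit 3, according to group. Neither definition asks for a baseline titer.

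On missing data, SAP 3.1.2, which covers the Visit 1 titers as well as the later ones, says "Missing assay results will not be imputed". SAP 5.3 adds: "No additional imputation will be applied unless stated otherwise". SAP 2.1 and Protocol 9.1.1 and 9.4.1 carry the same no-imputation rule for serology. Titers below the LLOQ are set to half the LLOQ, so a low baseline is not a missing one.

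For fold rises, Protocol 9.4.1 is explicit: "GMFRs will be limited to participants with nonmissing values both before any vaccination and after the indicated vaccination". It says the same for the 4-fold-rise percentage. No such sentence is visible for the GMR. Text is redacted after the model in SAP 5.2.2.2, SAP 6.1.2.1 and Protocol 9.4.1, and in SAP 5.3.

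**The concern.** The population named for the primary test is wider than the set of records the model can use. A participant with a perfectly good post-vaccination titer is lost from a serotype's noninferiority test for want of a covariate. The number lost will vary by serotype, and the visible text neither gives it nor acknowledges it.

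The contrast with fold rises sharpens the worry. The plan foresees missing baselines there, where a baseline is indispensable, and is silent on the GMR, which can be estimated without one. Noninferiority turns on the lower limit of a confidence interval for each serotype, so any avoidable widening counts against the vaccine. Serotype 8, with a GMR of 0.55 in the pivotal study, has no room to spare. One could also argue that who enters a primary model should be written down before unblinding.

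**Working it through.** **1. What the visible text implies.** The model needs a baseline titer, missing titers are not imputed, and ordinary linear regression uses only complete records. The three together give a complete-case analysis for each serotype. Two analysts following the text would obtain the same set of participants.

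**2. Reproduce the plan's figures.** Log-scale SDs follow from Protocol Table 4 as ln(U/L)/(2 × 1.96) × √n.

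- Serotype 8, 20vPnC: ln(591.0/493.9)/3.92 × √1374 = 1.70.
- Serotype 8, control: ln(1066.8/896.8)/3.92 × √1319 = 1.61.
- SE of the log GMR at 630 per group: √((1.70² + 1.61²)/630) = 0.093.
- Distance from the margin: ln(540.2/978.1) − ln(0.5) = 0.0995.
- Power: Φ(0.0995/0.0932 − 1.96) = Φ(−0.89) = 18.6%.

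Serotype 8 dominates the probability of success on all 20 serotypes, which Table 5 also puts at 18.6%. Simulating the 20 mean differences with an assumed common between-serotype correlation of 0.3 gives 94.7% for at least 19 of 20, as in Table 5.

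**3. Remove a share m for missing baseline.** The documents do not give m, so it is an assumption. The number left is 630(1 − m) per group, and interval width grows by 1/√(1 − m) − 1. SDs are kept unadjusted, as in Table 4.

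| m | n per group | CI wider by | Serotype 8 power | Serotype 6A power | At least 19 of 20 |
|---|---|---|---|---|---|
| 0 | 630 | – | 18.6% | 97.0% | 94.7% |
| 1% | 624 | 0.5% | 18.5% | 96.8% | not run |
| 2% | 617 | 1.0% | 18.3% | 96.7% | 94.3% |
| 5% | 599 | 2.6% | 17.9% | 96.2% | 93.2% |
| 10% | 567 | 5.4% | 17.2% | 95.4% | 91.6% |

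**4. Credit the adjustment.** The table overstates the loss, because the covariate that costs participants also removes variance. With baseline/post correlation r on the log scale, the complete-case variance relative to an unadjusted analysis of everyone is (1 − r²)/(1 − m). It is below 1 whenever r² > m, that is r above 0.22 at m = 5% and 0.32 at m = 10%.

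**5. Compare with filling the missing baseline by the serotype mean over both groups.** The variance with the fill is proportional to 1 − r²(1 − m); for complete cases it is proportional to (1 − r²)/(1 − m). The square root of complete-case over fill gives:

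- m = 1%: complete-case intervals 0.5% wider at r = 0.3, 0.3% wider at r = 0.5.
- m = 5%, r = 0.3: √(0.91/(0.95 × 0.9145)) = 1.023, so 2.3% wider; at r = 0.5, 1.8% wider.
- m = 10%: 4.9% wider at r = 0.3, 3.7% wider at r = 0.5.
- m = 5%, r = 0.8: √(0.36/(0.95 × 0.392)) = 0.983, so complete-case is 1.7% narrower.

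The two are equal at r² = 1/(2 − m), about r = 0.71 for small m. Above that, filling loses precision.

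**6. Bias.** Protocol 8.11.1 has baseline blood taken before vaccination. Site staff at Vaccination 1 and the serology laboratory are blinded (Protocol 6.3.2, 6.3.3). Missing baselines should therefore be unrelated to vaccine group, and the comparison among participants with a baseline remains a randomized one.

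**The case for a change.** The strongest reply is that the missing share may not be small for every serotype. Table 4 counts only valid, determinate results, and its 20vPnC counts run from 1430 (serotype 1) down to 1157 (serotype 33F), a shortfall of 1 − 1157/1430 = 19%. These are post-vaccination counts, so they are not baseline rates, but they show that usable OPA results vary by serotype and are fewest among the seven additional ones.

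That deserves a check. Suppose each serotype in each group loses the same share as its Table 4 shortfall from the serotype 1 count. At an assumed between-serotype correlation of 0.3, the chance of at least 19 of 20 falls only from 94.7% to 94.4%, and of all 20 from 18.3% (the simulated value with no loss) to 17.7%. The heavy shortfalls are in serotypes whose GMRs are 1.41 or more, where power is about 100% anyway. Serotype 8 itself shows shortfalls of 3.9% and 7.0%.

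It also stands that complete-case handling is implied and not stated, and that the visible text does not say the baseline titer enters on the log scale. SAP 5.2.2 fixes the natural log for OPA outcomes, and an analyst would treat the covariate likewise. A sentence on each, with model N by serotype and group, would be tidy. Both are detail that competent programming supplies, and redacted text may already contain it.

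**Conclusion.** No change is needed. The mismatch between the model and the evaluable definitions is real, but the no-imputation rule resolves it into one determinate analysis. That analysis errs, if at all, toward wider intervals, which is the cautious direction for a noninferiority claim.

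The expected loss is small: intervals 0.5% to 2.6% wider if 1% to 5% of baselines are missing, before any credit for covariate adjustment. This rests on an assumed missing share, on missingness unrelated to titer and group, and on the SDs and GMRs of Table 4. Even at an assumed 10%, serotype 6A keeps 95.4% power and serotype 8 loses 1.4 percentage points (18.6% to 17.2%) from a figure that was already low for other reasons.

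Replacing complete cases by a mean fill is not justified from the documents. Its benefit depends on a missing rate and a correlation they do not report, and it reverses above a correlation of about 0.71. It would also require an exception to the no-imputation wording in SAP 2.1 and 3.1.2 and Protocol 9.1.1 and 9.4.1, and possibly a protocol amendment if judged a major modification of the primary analysis.

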## Overall Design

This Phase 3, multicenter, randomized, double-blind study will be conducted at investigator sites in Japan, Korea, and Taiwan.

Approximately 1400 participants 60 years of age and older at enrollment will be randomized into 2 groups in a 1:1 ratio by center-based randomization: 20vPnC/saline group and 13vPnC/PPSV23 group. Each participant will be randomized to receive either 20vPnC or 13vPnC (control vaccine) at Vaccination 1. Participants who received 20vPnC at Vaccination 1 in the 20vPnC/saline group will receive saline at Vaccination 2. Participants who received 13vPnC at Vaccination 1 in the 13vPnC/PPSV23 group will receive PPSV23 at Vaccination 2.

On Day 1 (Visit 1), participants will be assessed for eligibility, have blood drawn for immunogenicity assessments, and receive 20vPnC or 13vPnC administered by blinded site staff. Participants will be observed for at least 30 minutes after vaccination by blinded site staff, who will record AEs occurring during that time. Participants will also receive safety follow-up and e-diary instructions at the visit. Prompted systemic events (fever, headache, fatigue, muscle pain, and joint pain) occurring within 7 days after vaccination and prompted local reactions (redness, swelling, and pain at the injection site) occurring at the 20vPnC or 13vPnC injection site within 10 days after vaccination will be collected daily in the e-diary. Use of antipyretic/pain medications will be collected daily in an e-diary for 7 days after vaccination.

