#### **4.1.2. Approximate Number of Participants**

Approximately 1400 participants will be enrolled to achieve a target of 1260 evaluable participants (630 participants in each vaccine group) (assuming a 10% nonevaluable rate). Approximately 700 participants will be enrolled from Japan, approximately 500 from Korea, and approximately 200 from Taiwan. The study will target enrolment of 50 %, or more, adults  $\geq 65$  years of age in each country. Note however, that the enrolment targets are approximations, and may not be achieved, particularly for the older age group. Randomization into the 2 vaccine groups will be managed within the age stratification (50 to 64 years of age and  $\geq 65$  years of age).

Note: "Enrolled" means a participant's agreement to participate in a clinical study following completion of the informed consent process. Potential participants who are screened for the purpose of determining eligibility for the study, but do not participate in the study, are not considered enrolled, unless otherwise specified by the protocol.

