##### **Type of Participant and Disease Characteristics:**

2. Participants who are willing and able to comply with all scheduled visits, treatment plan, lifestyle considerations, and other study procedures.
3. Expected to be available for the duration of the study and can be contacted by telephone during study participation.
4. Adults determined by clinical assessment, including medical history and clinical judgment, to be eligible for the study, including adults with preexisting stable disease, defined as disease not requiring significant change in therapy in the previous 6 weeks or hospitalization for worsening disease within 12 weeks before receipt of study intervention.

[For adults **60 through 64 years of age** to be enrolled **at Japan sites only**:]

- Participants must have a preexisting chronic stable disease with an elevated risk for pneumococcal disease (eg, chronic cardiac disease, chronic pulmonary disease, chronic hepatic disease, diabetes mellitus, and/or chronic renal disorders).

5. Female participants of nonchildbearing potential or male participants not able to father children; male participants who are able to father children and willing to use a highly

effective method of contraception as outlined in this protocol until at least 28 days after the last dose of study intervention.

COI

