### 9.4.1. Immunogenicity Analyses

The statistical analysis of immunogenicity results will be primarily based on the evaluable 13-matched immunogenicity and evaluable 7-additional immunogenicity populations (primary immunogenicity population) as defined in Section 9.3.

CCI [REDACTED]

Participants will be summarized according to the vaccine group to which they are randomized for analysis based on immunogenicity populations. Missing serology data will not be imputed. Titers below LLOQ or denoted as BLQ will be set to  $0.5 \times \text{LLOQ}$  for analysis.

Endpoint	Statistical Analysis Methods
Primary immunogenicity	
 
GMRs of pneumococcal serotype-specific OPA titers 1 month after vaccination 
 
(1) For each of the 13 matched serotypes, the ratio of the GMT 1 month after 20vPnC in the 20vPnC/saline group to the GMT 1 month after 13vPnC in the 13vPnC/PPSV23 group (Visit 2) will be provided;
 
(2) For each of the 7 additional serotypes, the ratio of the GMT 1 month after 20vPnC in the 20vPnC/saline group (Visit 2) to the GMT 1 month after PPSV23 in the 13vPnC/PPSV23 group (Visit 3) will be provided.
 
 
 

Endpoint	Statistical Analysis Methods
	
As the primary approach to calculate the GMR and CI for each serotype for OPA titer, a linear regression model that includes terms for age, corresponding baseline OPA titer, sex, smoking status, country, and vaccine group will be used to calculate the serotype-specific OPA GMR and 2-sided 95% CI, along with the model-based least squares GMTs and associated 2-sided 95% CIs, for each vaccine group. CCI
 
[REDACTED]
 
[REDACTED]
 
Hypothesis testing for NI of 20vPnC to the control vaccine (13vPnC for the 13 matched serotypes or PPSV23 for the 7 additional serotypes) will be performed as described in Section 9.1.2.1.

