2.2. Study Design

This Phase 3, multicenter, randomized, double-blind study will be conducted at investigator sites in Japan, Korea, and Taiwan.

Approximately 1400 participants 60 years of age and older at enrollment will be randomized into 2 groups in a 1:1 ratio by center-based randomization, stratified by age (60 through 64 years of age and ≥ 65 years of age), and assigned to either the 20vPnC/saline group or the 13vPnC/PPSV23 group. Each participant will be randomized to receive either 20vPnC or 13vPnC (control vaccine) at Vaccination 1. Participants who receive 20vPnC at Vaccination 1 in the 20vPnC/saline group will receive saline at Vaccination 2. Participants who received 13vPnC at Vaccination 1 in the 13vPnC/PPSV23 group will receive PPSV23 at Vaccination 2.

On Day 1 (Visit 1), participants will be assessed for eligibility, have blood drawn for immunogenicity assessments, and receive 20vPnC or 13vPnC administered by blinded or unblinded site staff. Participants will be observed for at least 30 minutes after vaccination by blinded site staff, who will record AEs occurring during that time. Participants will also receive safety follow-up and e-diary instructions at the visit. Prompted systemic events (fever, headache, fatigue, muscle pain, and joint pain) occurring within 7 days after vaccination and prompted local reactions (redness, swelling, and pain at the injection site) occurring at the 20vPnC or 13vPnC injection site within 10 days after vaccination will be collected daily in the e-diary. Use of antipyretic/pain medications will be collected daily in an e-diary for 7 days after vaccination.

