3.4.1. Demographics, Smoking History, and Medical History

The demographic variables are age at vaccination at Visit 1 (in years), age group (60 to 64 years or 65 years and older), sex (male or female), race (Black/African American, American Indian or Alaskan native, Asian, Native Hawaiian or other Pacific Islander, White, or not reported), racial designation (Japanese, Korean, Taiwanese, or Other), country (Japan, Korea, or Taiwan), and ethnicity (Hispanic/Latino, non-Hispanic/non-Latino, or not reported). In cases where more than 1 category is selected for race, the participant will be counted under the category “multiracial” for analysis.

Age in years at the first vaccination will be derived based on the participant’s birthday. For example, if the vaccination date is 1 day before the participant’s 65th birthday, the participant is considered to be 64 years old. For participants who are randomized but not vaccinated, the randomization date will be used in place of the date of the first vaccination for age calculation. If the randomization date is also missing, then the informed consent date will be used for age calculation.

Smoking history will be recorded as “current smoker,” “ex-smoker,” and “never smoked.” Start and stop dates for an ex-smoker and start date for a current smoker will be recorded on the CRF. Elapsed time since an ex-smoker stopped smoking will be summarized in years and derived as (Vaccination 1 date – stop date + 1)/365.25. Elapsed time since a current smoker started smoking will be derived as (Vaccination 1 date - start date + 1)/365.25. The midpoint value will be used to impute a partial date to the full date.

Demographic and disposition tables will be categorized by vaccine group. In addition, separate demographic tables by enrollment country and age group (60 through 64 years of age or 65 years of age and above) will be provided.

Medical history will be categorized according to MedDRA. Significant findings from any physical examination performed at baseline will also be collected on the medical history page of the CRF and summarized with the medical history.

CCI

CCI

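### The primary GMR model adjusts for country and age but not for centre or the randomisation age stratum: a small, conservative loss of precision

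*SAP*

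**What the plan says.** **Randomisation.** SAP 2.2 describes allocation in a "1:1 ratio by center-based randomization, stratified by age (60 through 64 years of age", the second stratum being 65 years and over. The protocol synopsis (Overall Design) also has participants "randomized into 2 groups in a 1:1 ratio by center-based randomization". Protocol 4.1.2 confirms the age stratification but prints a different lower band: "Randomization into the 2 vaccine groups will be managed within the age stratification (50 to 64 years of age". Entry is at 60 or over, so the SAP's 60–64 band is the one consistent with eligibility.

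**Primary model.** Protocol 9.4.1 specifies "a linear regression model that includes terms for age, corresponding baseline OPA titer, sex, smoking status, country, and vaccine group". SAP 5.2.2.2 lists the baseline titer and "age, sex (male or female), country (Japan, Korea, or Taiwan), smoking status (current smoker, ex-smoker, or never smoked), and vaccine group", and SAP 6.1.2.1 names the same terms. Sex, country and smoking status are given with their categories; age is not. SAP 3.4.1 lists two separate variables, "age at vaccination at Visit 1 (in years), age group (60 to 64 years or 65 years and older", so the model's age term reads as continuous, although the model text does not say so. Centre is not a term, and no visible text explains why.

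**A design feature at age 65.** Protocol 5.1 adds a condition for those aged 60–64 at Japan sites only: "Participants must have a preexisting chronic stable disease with an elevated risk for pneumococcal disease". Participants of 65 or over need not have one. Japan supplies about 700 of the 1400 participants.

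**The concern.** Restricted randomisation balances the arms on the factors it uses. If such a factor also predicts titer and the model omits it, the model-based standard error counts as noise some variation that the design has already removed from the comparison. The interval is then wider than it need be.

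The terms already present are only partial substitutes. Each centre lies in one country, so country absorbs differences between countries but none between centres within a country. A single age slope cannot follow a jump at 65, and the Japan eligibility rule makes a jump there possible if chronic disease affects OPA response. The documents do not show whether it does.

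Each serotype is judged on its lower 95% bound against 0.5, so what is at stake is precision in the primary analysis. It matters most for serotype 8, and for 6A and 23F, the matched serotypes with the least room.

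**Working it through.** **1. Reproducing the plan's figures.** The inputs are the GMTs, CIs and sample sizes in protocol Table 4, with 630 evaluable per group (protocol 9.2).

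- Log SD per arm = ln(upper/lower) / (2 × t) × √n. Serotype 8, 20vPnC/saline: ln(591.0/493.9), n = 1374, gives 1.696. Serotype 8, 13vPnC/PPSV23: ln(1066.8/896.8), n = 1319, gives 1.607.
- SE at 630 per group = √((1.696² + 1.607²)/630) = 0.0931.
- GMR = 540.2/978.1 = 0.5523, so ln(0.5523) − ln(0.5) = 0.0995.
- Power = Φ(0.0995/0.0931 − 1.96) = 18.6%. The same formula gives 97.0% for 6A and 98.0% for 23F.
- Joint probabilities need the correlation between serotypes, which is not given. With an assumed common correlation of 0.4, success on ≥18, ≥19 and all 20 serotypes is 99.3%, 94.8% and 18.6%. Protocol 9.2 states 99.3%, 94.7% and 18.6%, so the figures are reproduced.

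Table 4 uses unadjusted differences in log titers. The planned probabilities therefore assume no covariate adjustment at all.

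**2. The age stratum alone.** No step size at 65 is given; take 0.3 log units, in Japan only, as an assumption. With half the sample in Japan and a 50/50 age split, the variance explained is about 0.3² × 0.25 × 0.5 = 0.011. The serotype 8 variance is (1.696² + 1.607²)/2 ≈ 2.73, so the share is about 0.4% and the SE gain about 0.2%, before linear age absorbs any of it. A simulation of 1260 participants, randomised in blocks within centre and stratum (300 replicates per scenario), agrees. Adding the stratum to a model with baseline titer, linear age and country gives an SE ratio of 1.000 if the age effect is linear, and 0.995–0.998 with a true step of 0.3–0.5 log units.

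**3. Stratum plus centre.** The number of centres (assumed 20–60) and the centre share of residual variance (assumed 0–5%) are not in the documents. As an approximation, SE ratio ≈ √(1 − share).

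| Centre share | √(1 − share) | Simulated SE ratio |
|---|---|---|
| 0 | 1.000 | 0.995–1.003 |
| 2% | 0.990 | 0.986–0.993 |
| 5% | 0.975 | 0.972–0.979 |

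With no centre effect and 60 fixed centre terms, the interval is up to about 0.25% wider.

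**4. Consequence for the decision, at the most favourable ratio, 0.972.**

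- Serotype 8 lower bound at its planning GMR: exp(−0.5937 − 1.96 × 0.0931) = 0.460 becomes exp(−0.5937 − 1.96 × 0.972 × 0.0931) = 0.463. Both are below 0.5.
- Serotype 8 power: 18.6% to 19.5%.
- Success on ≥18, ≥19 and all 20: 99.6%, 96.1% and 19.4%. The risk of missing ≥19 falls from 5.2% to 3.9%.

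These shifts apply the ratio to the unadjusted planning variances, so they illustrate the size of the gain and do not predict power under the adjusted model.

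**The case against.** The strongest reply is that very little is missing. Age and country are in the model, and linear age captures nearly all of what the stratum would add. The remaining gain comes from a centre variance that has to be assumed; with none, the change costs a trace of precision. No serotype's outcome is shown to turn on it. The ≥19/20 probability is already about 95%, and protocol 9.2 itself attributes the low 20/20 figure to the serotype 8 GMR. All of this stands, and it sets the weight of the point.

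Three stronger readings are tempting and are not supported:

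- That the model leaves out both randomisation factors, or that its intervals ignore the randomisation. Age is a term, and country captures the between-country part of centre.
- That the intervals are wider than the design allows. Planning used unadjusted variances, and the planned covariates would be expected to narrow the intervals relative to that basis.
- That the noninferiority conclusions are unsafe. Omitting a prognostic balanced factor makes the intervals too wide, which works against declaring noninferiority.

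SAP 5.2.2.2 announces two approaches and the second is blacked out, so a supporting analysis with centre may exist. That does not alter the primary model, which is visible.

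**Conclusion.** The point holds in a modest form. Centre, the unit within which participants are randomised, and the age stratum as randomised are absent from the primary model, and no visible text gives a reason. If centre is prognostic within country, the noninferiority intervals are slightly too wide: about 1–3% in SE at an assumed 2–5% centre share. Nearly all of that comes from centre. The direction is conservative and there is no type I error problem. No rescue of serotype 8 should be expected. The size rests on assumed centre numbers, centre variance and step at 65, none of which the documents give. The case for acting is that the trial already bears the cost of randomising on these factors, and using them in the analysis is nearly free.

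**What to change.** In SAP 5.2.2.2 and 6.1.2.1 and protocol 9.4.1:

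- State that age enters as a continuous covariate in years.
- Add the randomisation age stratum (60–64 / ≥65) as recorded at allocation.
- Add centre as a random intercept or, to stay within ordinary linear regression, as a fixed factor with small centres pooled within country. Fixed centre effects make the country main effect redundant, so the text should say how country is then handled.
- Reconcile the protocol's 50–64 band with the SAP's 60–64, so that the stratum term has one definition.

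**Cost.** The stratum takes one degree of freedom. A random intercept takes one variance parameter and turns the linear regression into a mixed model. Fixed centres take a few tens of degrees of freedom out of about 1260 and need a pooling rule. Intervals could be up to about 0.25% wider if there is no centre effect. This is more than a line of SAP text: protocol section 9 and SAP section 2 both require major changes to the primary analysis to be reflected in a protocol amendment, so a matching protocol update should be planned. The change should be made before unblinding and database lock.
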